5.1.2.2. Psoriasis Specific Inclusion Criteria

1. Participants with a diagnosis of plaque psoriasis (psoriasis vulgaris) for at least 6 months prior to Day 1.
2. Participants with a Physician Global Assessment (PGA) score of 2 (mild), or 3 (moderate) at Screening and Day 1. Note: Refer to [Section 8.1.4.2](#) for the assessment of 5-point PGA.
3. Having plaque psoriasis covering 5% to 15% (inclusive) of BSA (excluding the scalp) at both the Screening and Day 1/Randomization. Note: Refer to [Section 8.1.4.3](#) for detailed methods of calculating treatable BSA.

5.2. Exclusion Criteria

The exclusion criteria for AD and psoriasis are the same.

Participants are excluded from the study if any of the following criteria apply:

Medical Conditions:

1. Presence of skin comorbidities that would interfere with study assessment or response to treatment.

2. Any psychiatric condition including recent or active suicidal ideation or behavior that meets any of the following criteria at Screening or Day 1:
 - a. Suicidal ideation associated with actual intent and/or plan in the past year: “Yes” answers on items 4 “some intent to act without specific plan” or 5 “specific plan and intent” of the Columbia Suicide Severity Rating Scale (C-SSRS);
 - b. Previous history of suicidal behaviors in the past 5 years: “Yes” answer (for events that occurred in the past 5 years) to any of the suicidal behavior items of the C-SSRS;
 - c. Any lifetime history of serious or recurrent suicidal behavior;
 - d. The presence of any current major psychiatric disorder that is not explicitly permitted in the inclusion/exclusion criteria;
 - e. In the opinion of the investigator or Pfizer (or designee) exclusion is required.
3. Current or recent history (within approximately 3 months prior to Day 1) of severe, progressive, or uncontrolled renal, hepatic, hematological, gastrointestinal, metabolic, endocrine, pulmonary, cardiovascular, or neurological disease.
4. A history of systemic (within approximately 3 months prior to Day 1), chronic or acute skin infection (within approximately 2 weeks prior to Day 1) requiring hospitalization, parenteral antimicrobial therapy, or as otherwise judged clinically significant by the investigator.
5. A known immunodeficiency disorder or a first degree relative with a hereditary immunodeficiency.
6. Undergone significant trauma or major surgery within 1 month prior to screening.
7. Have a history of cancer within 5 years or has undergone treatment for any type of cancer, with the exception of adequately treated or excised non-metastatic basal cell or squamous cell cancer of the skin or cervical carcinoma in situ with no evidence of recurrence.
8. Have a history of angioedema or anaphylaxis to topical products or known sensitivity to any of the components of the investigational products.
9. Other medical or psychiatric condition including recent (within the past year) or active suicidal ideation/behavior or laboratory abnormality that may increase the risk of study participation or, in the investigator’s judgment, make the participant inappropriate for the study.

Prior/Concomitant Therapy:

10. Has received any of the prohibited medications/therapies that may alter the course of the diseases under study without the required minimum washout period or anticipated concomitant use of any of the prohibited medications/therapy (see [Appendix 10](#)).

Prior/Concurrent Clinical Study Experience:

11. Previous administration with an investigational drug within 30 days (or as determined by the local requirement) or 5 half-lives preceding the first dose of study intervention used in this study (whichever is longer).

Note: Any investigational or experimental therapy taken or procedure performed for AD, psoriasis, psoriatic arthritis or rheumatoid arthritis in the previous 1 year should be discussed with the Pfizer Medical Monitor (or designee). Participants cannot participate in studies of other investigational or experimental therapies or procedures at any time during their participation in this study.

Diagnostic Assessments:

12. Baseline 12 lead ECG that demonstrates clinically relevant abnormalities that may affect participant safety or interpretation of study results (eg, QTc interval >450 msec, complete LBBB, signs of an acute or indeterminate-age myocardial infarction, ST-T interval changes suggestive of myocardial ischemia, second or third degree AV block, or serious bradyarrhythmias or tachyarrhythmias). If the baseline uncorrected QT interval is >450 msec, this interval should be rate-corrected using the Fridericia method and the resulting QTcF should be used for decision making and reporting. If QTc exceeds 450 msec, or QRS exceeds 120 msec, the ECG should be repeated 2 more times and the average of the 3 QTc or QRS values should be used to determine the participant's eligibility. Computer-interpreted ECGs should be overread by a physician experienced in reading ECGs before excluding participants.
13. Participants with ANY of the following abnormalities in clinical laboratory tests at Screening, as assessed by the study specific laboratory and confirmed by a single repeat (the last value will be used to determine eligibility), if deemed necessary:
 - a. Estimated glomerular filtration rate (eGFR) <60 mL/min/1.73 m²;
 - b. Aspartate aminotransferase (AST) or alanine aminotransferase (ALT) values ≥ 2 times the ULN;
 - c. Total bilirubin ≥ 1.5 times the ULN; participants with a history of Gilbert's syndrome may have a direct bilirubin measured and would be eligible for this study provided the direct bilirubin is \leq ULN.

14. In the opinion of the investigator or sponsor, have any uncontrolled clinically significant laboratory abnormality that would affect interpretation of study data or the participant's participation in the study.

Other Exclusions:

15. Investigator site staff or Pfizer employees directly involved in the conduct of the study, site staff otherwise supervised by the investigator, and their respective family members.
16. A history of alcohol or substance abuse within 6 months prior to Screening that in the opinion of the investigator will preclude participation in the study.
17. In the opinion of the investigator or Sponsor Clinician or Sponsor Medical Monitor, the participant is inappropriate for entry into this study.

5.3. Lifestyle Considerations

5.3.1. Contraception

The investigator or his or her designee, in consultation with the participant, will confirm that the participant has selected an appropriate method of contraception for the individual participant and his or her partner(s) from the permitted list of contraception methods (see [Appendix 4 Section 10.4.4](#)) and will confirm that the participant has been instructed in its consistent and correct use. At time points indicated in the *SoA*, the investigator or designee will inform the participant of the need to use acceptable effective contraception consistently and correctly and document the conversation and the participant's affirmation in the participant's chart (participants need to affirm their consistent and correct use of at least 1 of the permitted methods of contraception). In addition, the investigator or designee will instruct the participant to call immediately if the selected contraception method is discontinued or if pregnancy is known or suspected in the participant or partner.

5.3.2. Dietary Supplements

For the purposes of this protocol, dietary supplements are defined as vitamins, minerals, purified food substances, and herbals with pharmaceutical properties. Vitamins, minerals and purified food substances are allowed in amounts not known to be associated with adverse effects (such as hypervitaminosis). Herbals supplements are only allowed on a case by case basis; please contact the Pfizer staff. Herbals eg, St. John's Wort that are known to have an effect on drug metabolism must be discontinued at least 4 weeks or 5 half-lives (whichever is longer) before Day 1.

5.3.3. Medications/Treatments Discontinuation, Non-Medicated Emollients

Participants are required to discontinue and avoid using certain medications and treatments as described in [Section 10.10 Appendix 10](#). Prohibited Prior and Concomitant Medications including medications which may result in Drug-Drug Interaction (DDI).

All topical medications and treatments that could affect atopic dermatitis and psoriasis skin areas must be discontinued for the duration of the study, if the skin areas are to be treated with IP.

Unless specified in [Appendix 10](#), any other concomitant medication for AD or psoriasis will be considered on a case by case basis by the investigator in consultation with the Sponsor Medical Monitor.

Non-medicated emollient and sunscreen are the only topical products permitted to be used on AD and psoriasis skin during the Screening period. Participants will stop applying non-medicated emollient and sunscreen on atopic dermatitis/psoriatic skin 24 hours prior to Day 1/Randomization. During the study treatment period, use of non-medicated emollient and sunscreen are allowed only on skin that was considered normal or non-lesional at Day 1 (ie, never treated with IP). Any non-medicated emollient used by the participant during the study should be documented in study records and the Case Report Form (CRF).

Low or least potent (Class 6 or 7) topical corticosteroids (Hydrocortisone $\leq 1\%$ and hydrocortisone acetate $\leq 1\%$) are the only topical corticosteroids permitted for the treatment of areas never treated with IP (eg, palms, soles, face, and intertriginous). Scalp tar preparations, salicylic acid preparations and shampoos free of corticosteroids are permitted for the treatment of scalp.

Due to the potential to affect atopic dermatitis and psoriasis with ultraviolet light exposure, participants must avoid prolonged exposure to the sun and avoid the use of tanning booths, sun lamps or other ultraviolet light sources during the study. Please see [Appendix 10](#) for details on prohibited light therapy.

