6.1.1. Administration

6.1.1.1. Treatable Areas

AD treatable areas will be all areas affected by AD, except scalp.

Psoriasis treatable areas will be all areas affected by psoriasis, except scalp and nails.

A thin layer of IP ointment will be applied at a target application rate of approximately 3 mg/cm² by using a fingertip unit (FTU) method.

Day 1 Visit

At the Day 1 Visit, before the Day 1 initial IP application is performed, the designated areas for treatment will be identified and documented in the participant's source document study records (body map). The participant and/or caregiver will be provided with a paper version of the body map.

On Day 1 through the final dose at Week 6 visit, the IP should be applied once daily (around same time of the day), to all treatable AD or psoriasis involved areas identified at the Day 1 visit.

All participants will be supplied with instructions on application and dose frequency commensurate to assigned treatment arm. Those participants having difficulty reaching treatment-eligible areas (eg, back) may be assisted by another person who will need to apply the IP to the participant according to the investigational product application instructions. The person assisting with the application must wear gloves to avoid any exposure to the IP.

Participants and/or caregivers will be encouraged to observe and participate in the initial IP application on Day 1.

Post Day 1 Visits

After Day 1/Randomization, all subsequent doses will be applied at home except the dose on the days of in-clinic visits. CCI

The last dose of IP will be applied during the Week 6 in-clinic visit (EOT visit) as specified in [Section 1.3.3](#) of the [SoA](#).

The participant and/or caregiver will be instructed to complete the Dosing Diary starting with the first dose applied in the clinic on Day 1 through Week 6 (each time IP is applied) for all IP doses applied. If a participant misses applying a dose, the participant should apply this dose provided this dose should have been applied within the last 6 hours. For longer intervals, the dose should be skipped. The missed dose should be recorded in the dosing diary. The next dose should be applied according to the regular dosing regimen.

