8.1. Efficacy Assessments

8.1.1. Rater Qualifications

For specific rating assessments, only qualified raters will be allowed to evaluate and/or rate participants in this study. The minimum qualifications a rater must meet for each study rating assessment will be outlined in the Rater Assessment Guide provided to each participating site. The level of experience with the target population (or equivalent), specific scale experience (or equivalent), and certification required (if applicable) will be listed and used to determine whether a rater is approved for a given assessment. Proposed raters who do not meet specific criteria but who may be qualified based on unique circumstances may be individually reviewed by the study clinical team to determine whether or not a waiver may be issued. The rater must become certified to perform selected study assessments before he or she can participate in the conduct of the study. For specifically defined assessments, rater training and standardization exercises may be conducted, and written and signed documentation will be provided by the site for each rater's certification. In return, each site will be provided written and signed documentation outlining each rater's certification for specific study assessments. Recertification may be required at periodic intervals during the study. The raters who administer specific study assessments will be documented in a centralized location and all site staff who administer ratings will be verified in the site study documentation during the conduct of the study.

EFFICACY ASSESSMENTS FOR AD

All efficacy assessments will be based on areas treated with IP, and excluding scalp, palms and soles from the assessment/scoring.

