8.1.2. Physician Assessments for AD

8.1.2.1. Eczema Area and Severity Index (EASI)

The EASI quantifies the severity of a participant's AD based on both severity of lesion by clinical signs and the percent of BSA affected. EASI is a composite scoring of the degree of erythema, induration/papulation, excoriation, and lichenification (each scored separately) for each of four body regions, with adjustment for the percent of BSA involved for each body region and for the proportion of the body region to the whole body.⁸

Lesion Severity by Clinical Signs

The basic characteristics of AD lesions (erythema, induration/papulation, excoriation, and lichenification) provide a means for assessing the severity of lesions. Assessment of these four main clinical signs is performed separately for four body regions: head and neck, upper limbs, trunk (including axillae and groin) and lower limbs (including buttocks). Average erythema, induration/papulation, excoriation, and lichenification are scored for each body region according to a 4-point scale: 0 = absent; 1 = mild; 2 = moderate; 3 = severe. Morphologic descriptors for each clinical sign severity score are shown in [Table 5](#) below.

Table 5. Clinical Sign Severity Scoring Criteria for EASI

Score		Description
Erythema (E)		
0	Absent	None; may have residual discoloration (post-inflammatory hyperpigmentation and/or hypopigmentation)
1	Mild	Light pink to light red
2	Moderate	Red
3	Severe	Deep, dark red
Induration/Papulation (I)		
0	Absent	None
1	Mild	Barely palpable to slight, but definite hard thickened skin and/or papules
2	Moderate	Easily palpable moderate hard thickened skin and/or papules
3	Severe	Severe hard thickened skin and/or papules
Excoriation (Ex)		
0	Absent	None
1	Mild	Slight, but definite linear or picked scratch marks or penetrating surface injury
2	Moderate	Moderate linear or picked scratch marks or penetrating surface injury
3	Severe	Severe linear or picked scratch marks or penetrating surface injury
Lichenification (L)		
0	Absent	None
1	Mild	Barely perceptible to slight, but definite thickened skin, fine skin markings, and lichenoid scale
2	Moderate	Moderate thickened skin, coarse skin markings, and coarse lichenoid scale
3	Severe	Severe thickened skin with very coarse skin markings and lichenoid scale

* The EASI will exclude scalp, palms and soles from the assessment/scoring.

BSA with AD for EASI Assessment (excluding scalp, palms and soles)

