8.1.2.3. BSA with AD

Assessment of BSA involved in AD is performed separately for four areas of the body: head (including neck), upper limbs, trunk (including axillae and groin), and lower limbs (including buttocks). The percentage surface area affected by AD is estimated by means of the “handprint method”, where the full hand of the participant (ie, the participant’s fully extended palm, fingers and thumb together) represents approximately 1% of the total BSA. Refer to [Table 6](#) to identify the surface area equivalent of 1 handprint in each respective body region.

Body region value is then summed across all four body regions resulting in a total BSA with AD as described in the following equation:

$$\text{BSA (\%)} = 0.1S_h + 0.2S_u + 0.3S_t + 0.4S_l$$

where S = body region surface area with AD; h = head & neck; u = upper limbs; t = trunk; l = lower limbs.

BSA with AD for Efficacy Assessment (Efficacy BSA)

BSA with AD for efficacy evaluation excludes scalp, palms, and soles.

BSA with AD for IP Need (Treatable BSA)

Evaluation of BSA for IP need is the total BSA across all body locations being treated with the IP. BSA for IP need evaluation method will be the same as the BSA with AD for efficacy assessment, except that the BSA for IP need will include AD on all IP treated body locations (including palms and soles but not scalp). If a participant has AD on palms, and/or soles, these body locations will be included in the BSA for IP need estimation.

Investigational product should be applied to the BSA determined at Day 1 throughout the treatment period regardless of clearing or improvement of AD. Any new AD on treatment-eligible locations occurring after Day 1 should also be treated with the IP. Therefore, the BSA for IP requirements at subsequent visits should be equal to or greater than the value at Day 1.

A checklist of body site areas currently affected by AD (body map) will be completed at the Day 1 visit. The body map will be reviewed at every visit to the site to update for any new, treatable areas, if needed.

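### Protocol 5.3.3 lists palms, soles, face and skin folds as sites that never receive IP, but 6.1.1.1 makes them treatable, so treated skin, and for face and folds scored skin, can differ between sites

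*Protocol*

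**What the plan says.** **Concomitant treatment.** Protocol 5.3.3 says of class 6 or 7 steroids (hydrocortisone or hydrocortisone acetate, up to 1%) that they "are the only topical corticosteroids permitted for the treatment of areas never treated with IP (eg, palms, soles, face, and intertriginous". The same section says that other topical treatments "must be discontinued for the duration of the study, if the skin areas are to be treated with IP".

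**IP application.** Protocol 6.1.1.1 states "AD treatable areas will be all areas affected by AD, except scalp" and "Psoriasis treatable areas will be all areas affected by psoriasis, except scalp and nails". New lesions on eligible skin are also to be treated, after assessment by the investigator or a designee.

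**Treatable BSA.** Protocol 8.1.2.3 states "If a participant has AD on palms, and/or soles, these body locations will be included in the BSA for IP need estimation". Section 8.1.4.3 says the same for psoriasis.

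**Scoring.** The introduction to the AD assessments, at the end of 8.1.1, states "All efficacy assessments will be based on areas treated with IP, and excluding scalp, palms and soles from the assessment/scoring". The matching introduction for psoriasis, just before 8.1.4, also limits scoring to IP-treated skin and adds nails to the exclusions. The footnote to the EASI table in 8.1.2.1 reads "The EASI will exclude scalp, palms and soles from the assessment/scoring". Sections 8.1.2.1 and 8.1.4.1 both say that palms and soles stay out of the score even where they receive IP.

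**The concern.** An investigator who reads 5.3.3 learns that palms, soles, face and intertriginous skin are typical sites without IP, where a mild steroid may be used. One who reads 6.1.1.1 learns that the same sites get IP if they are affected. Both readers are following the protocol.

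Two things are at stake. The first is which skin receives IP or a steroid, and so how much IP is dispensed and what the treatable BSA is. That BSA feeds the entry criteria and the limits of 22% (AD) and 16.5% (psoriasis) during treatment. The second is the content of EASI and PASI, because scoring follows the IP-treated area. The face lies in the head and neck region, and axillae and groin lie in the trunk region. Both regions are scored.

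**Working it through.** The plan states no figure on this point, so the check is a comparison of the passages followed by an illustration with the protocol's own formulas.

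**Step 1: passages side by side (affected skin)**

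| Site | 5.3.3 | 6.1.1.1 | Treatable BSA (8.1.2.3, 8.1.4.3) | EASI/PASI |
|---|---|---|---|---|
| Palms, soles | no IP, mild steroid permitted | IP | included by name | never scored |
| Face | no IP, mild steroid permitted | IP | included if IP-treated | scored only if IP-treated |
| Axillae, groin | no IP, mild steroid permitted | IP | included if IP-treated | scored only if IP-treated |

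For palms and soles the conflict is explicit. For face and folds it follows from 6.1.1.1, which does not except them.

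**Step 2: EASI illustration.** Region value = region weight (Table 8) × area score (Tables 6 and 7) × sign total. Assumed pattern, not from the documents: one handprint on the face, one in the axilla or groin, two on the upper limbs, two on the lower limbs. All four signs are moderate, so the sign total is 4 × 2 = 8.

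- Head and neck: 10% of the region, area score 2, 0.1 × 2 × 8 = 1.6
- Upper limbs: 10%, area score 2, 0.2 × 2 × 8 = 3.2
- Trunk (fold only): 3.33%, area score 1, 0.3 × 1 × 8 = 2.4
- Lower limbs: 5%, area score 1, 0.4 × 1 × 8 = 3.2

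Baseline EASI is 1.6 + 3.2 + 2.4 + 3.2 = 10.4 with every site, 10.4 − 1.6 = 8.8 without the face, and 8.8 − 2.4 = 6.4 without face and fold. At 1% per handprint, BSA is 6%, 5% and 4%. The AD entry minimum is 5%.

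**Step 3: AD primary endpoint (percent change), area scores held fixed.** Let the sign total fall from 8 to 2.

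- Same response everywhere: 10.4 to 2.6 is −75%, and 6.4 to 1.6 is −75%. Dropping face and fold changes nothing.
- Limbs respond, face and fold do not change at all: with all sites scored, (1.6 + 4.0 − 10.4)/10.4 = −46%; with limbs only, −75%. This is an extreme case.

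**Step 4: psoriasis primary endpoint (absolute change).** PASI has three signs and the same area bands and weights. For the same pattern with each sign at 2, the sign total is 6. PASI is 1.2 + 2.4 + 1.8 + 2.4 = 7.8 with all sites and 2.4 + 2.4 = 4.8 on the limbs. If every sign falls from 2 to 1, the change is −3.9 against −2.4. An absolute change therefore depends on the scored skin even when all sites respond alike.

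**The case against.** The best defence is that 5.3.3 governs concomitant treatment, not IP application. It does not instruct a site to withhold IP. Treated skin is set by 6.1.1.1 and the treatable-BSA rules, which agree with each other, and it is recorded on a Day 1 body map. The list in 5.3.3 is only a set of examples. The same section elsewhere equates skin that never gets IP with skin that was normal at Day 1, and a new lesion may go without IP until it has been assessed.

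This lowers the chance that a site goes wrong but does not remove the contradiction. A steroid used to treat an area presupposes disease there. Under 6.1.1.1 affected skin at these four sites is treatable, so they are poor examples of diseased skin that never gets IP. The body map records whichever reading the site adopted.

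Three stronger readings are tempting, and the documents do not support them:

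- **Steroid benefit enters the score.** Low-potency hydrocortisone is not in the class I to V row of Appendix 10, so its use would not clearly trigger the rule that sets data to missing. But 5.3.3 permits it only on skin without IP, and efficacy scoring is limited to skin with IP. The restriction to treated areas and the excluded sites stand in one sentence and apply together. Steroid effect reaches EASI or PASI only if a site scores untreated skin against that rule.
- **All four sites change EASI and PASI.** Palms and soles are unscored under either reading.
- **The comparison is biased.** Allocation is randomized and double-blind within each indication, so differing site practice would be expected to affect both arms. Nothing in the documents shows a direction.

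**Conclusion.** Wrong as written: 5.3.3 contradicts 6.1.1.1 at all four sites, and contradicts 8.1.2.3 and 8.1.4.3 explicitly for palms and soles.

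For palms and soles the consequence is confined to treatment, IP quantity and treatable BSA. For face and folds it extends to the primary endpoints, because these sites are scored under 6.1.1.1 and unscored under 5.3.3. The expected harm is added heterogeneity between sites, in a trial planned on 21 evaluable AD participants and 12 evaluable psoriasis participants per arm.

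The effect on the trial result cannot be computed, because the documents do not say how many participants have facial or fold disease or how sites read the text. The figures above show only how far one participant's score can move, and they rest on the assumed pattern. The 2.4 points for the trunk apply only where the folds are the sole trunk involvement; with other trunk lesions the area score may not change. The fall to 4% BSA also requires that the site carry the 5.3.3 list into its BSA estimate. The stated power calculations are not affected.

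**What to change.** Reconcile 5.3.3 with 6.1.1.1, the scoring rule for AD at the end of 8.1.1, 8.1.2.1 and 8.1.2.3, and with the psoriasis counterparts (the rule just before 8.1.4, then 8.1.4.1 and 8.1.4.3). One list of IP-treated areas per indication should govern four things: where IP is applied, where a low-potency steroid is permitted, what counts as treatable BSA, and what is scored. Which list is correct is a clinical decision for the sponsor, and this review does not propose one.

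The cost is a protocol clarification and a communication to sites. No procedure, visit or sample size changes. If participants are already enrolled, the Day 1 body maps can show before unblinding which reading each site applied.
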